7.3.4 Reporting of Serious Adverse Events

Prompt notification by the investigator to the sponsor of an SAE is essential, so that legal obligations and ethical responsibilities towards the safety of subjects and the safety of a study intervention under clinical investigation are met.

In the case of an SAE, the investigator must contact the sponsor by fax or email immediately (within 24 hours of awareness).

Procedures for reporting SAEs to the sponsor are described in [Appendix 12.4.5 Reporting Procedures for Serious Adverse Events].

7.3.5 Disease-related Events and/or Disease-related Outcomes Not Qualifying as Adverse Events or Serious Adverse Events

Under this protocol, the following event(s) will not be considered as an SAE:

- Disease progression: events including defined study endpoints that are clearly consistent with the expected pattern of progression of the underlying disease are not to be recorded as AEs. These data will be captured as efficacy assessment data as outlined in [Section 7.1 Efficacy Assessments]. If there is any uncertainty as to whether an event is due to anticipated disease progression and/or if there is evidence suggesting a causal relationship between the IP and the event, it should be reported as an SAE. All deaths up to 30 days after the final IP administration must be reported as an SAE, even if attributed to disease progression.
- Preplanned and elective hospital/clinical procedures/interventions or procedures for diagnostic, therapeutic, or surgical procedures for a pre-existing condition that did not worsen during the course of the study. These procedures are collected per the electronic data source's completion guidelines.

7.3.6 Adverse Events of Special Interest

Adverse Events of Special Interest include:

- Increased blood pressure
- Cardiac electrophysiology (including QTc prolongation) and cardiac arrhythmia (including increased heart rate, tachycardia, atrial fibrillation and palpitations)
- Hypersensitivity reactions
- Urinary retention
- Hepatotoxicity
- Seizure/syncope

AEs (serious or nonserious) of special interest are to be collected via the SAE worksheet and reported within 24 hours as described in [Appendix 12.4.5 Reporting Procedures for Serious Adverse Events].

Sponsor: APGD EudraCT number 2016-001767-37 - CONFIDENTIAL -

ponsor: APGD ISN/Protocol: 178-CL-204

7.3.7 Special Situations

Certain special situations observed in association with the IP, such as incorrect administration (e.g., wrong dose of IP or background therapy) are collected in the electronic data source, as protocol deviation per [Section 10.3 Major Protocol Deviations] or may require special reporting, as described below. These special situations are not considered AEs, but do require to be communicated to Astellas as per the timelines defined below.

If a special situation is associated with, or results in, an AE, the AE is to be assessed separately from the special situation and captured as an AE in the electronic data source. If the AE meets the definition of an SAE, the SAE is to be reported as described in [Appendix 12.4.5 Reporting Procedures for Serious Adverse Events] and the details of the associated special situation are to be included in the clinical description on the SAE worksheet.

The special situations are:

- Pregnancy
- Medication error/overdose
- Misuse/abuse
- Occupational exposure
- Suspected drug-drug interaction

Instructions and procedures for reporting special situations are provided in [Appendix 12.4.6 Reporting Procedures for Special Situations].

7.3.8 Supply of New Information Affecting the Conduct of the Study

When new information becomes available that is necessary for conducting the study properly, the sponsor will inform all investigators involved in the study as well as the appropriate regulatory authorities. Investigators should inform the IRB/IEC of such information when needed.

The investigator will also inform the subjects, who will be required to sign an updated ICF/assent in order to continue in the study.

7.3.9 Urgent Safety Measures

An urgent safety measure (USM) is an intervention that is not defined by the protocol and can be put in place with immediate effect without needing to gain prior approval by the sponsor, relevant competent authorities and IRB/IEC, where applicable, in order to protect subjects from any immediate hazard to their health and/or safety. Either the investigator or the sponsor can initiate a USM. The cause of a USM can be safety-, product- or procedure-related.

7.3.10 Reporting Urgent Safety Measures

In the event of a potential USM, the investigator must contact the study physician (within 24 hours of awareness). Full details of the potential USM are to be recorded in the subject's

- CONFIDENTIAL -

medical records. The sponsor may request additional information related to the event to support their evaluation.

ISN/Protocol: 178-CL-204

If the event is confirmed to be a USM, the sponsor will take appropriate action to ensure the safety and welfare of the subjects. These actions may include but are not limited to a change in study procedures or study treatment, halting further enrollment in the study, or stopping the study in its entirety. The sponsor or sponsor's designee will notify the relevant competent authorities and concerned ethics committee within the timelines required per current local regulations, and will inform the investigators, as required. When required, investigators must notify their IRB/IEC within timelines set by regional regulations.

7.4 Pharmacokinetics

Blood samples for the analysis of mirabegron in plasma will be collected as indicated in the Schedule of Assessments [Table 1] for the evaluation of pharmacokinetics.

The actual date and time of each blood sample collection will be documented. Sample collection, handling and storage will be described in the laboratory manual. Bioanalysis of mirabegron will be performed using a validated method.

A topical anesthetic cream or plaster must be offered at the point of venipuncture to minimize distress of the subject. For sampling the arm opposite to the arm used for blood pressure measurements should be used (i.e., preferably the left arm). Blood sampling should occur after vital signs and ECG measurements.

The pharmacokinetic parameters that will be calculated as part of the secondary pharmacokinetic endpoint are steady-state C_{max}, AUC_{tau}, C_{trough}, T_{max}, CL/F and V_z/F. Additional parameters may be calculated based on the population pharmacokinetic model used.

7.5 Pharmacodynamics | Immunogenicity

Not applicable.

7.6 Electronic Clinical Outcome Assessment

For this study, it has been decided that there are justifiable scientific reasons (i.e., recall bias) to limit subject reported changes to changes reported by the subject to the site within 1 business day of its entry, as changes outside of this window could potentially impact the data integrity of the study. The data that will be under this rule are all subject/guardian/parent-entered primary and secondary endpoints data. However, the site/investigator can remove/inactivate any data that they determine to be in error at any time with source documentation to support the change including subject confirmation. Data will never be deleted from the electronic database by the electronic clinical outcome assessment (eCOA) service provider, but will be removed logically as per investigator's request and approval. All data changes are audit trailed showing the original entries alongside all changes including who requested the change, why it was requested, who made the change and when it was

- CONFIDENTIAL -

made. Audit trails are reviewed by the sponsor/clinical research organization (CRO) to ensure adherence to the protocol and appropriate source exists at site to substantiate the change.

ISN/Protocol: 178-CL-204

Subject bladder diaries, questionnaires and other data will be completed by the subject or the subject's parent(s)/legal guardian(s)/caregiver(s) on an electronic device (e-diary). The information on the electronic device will be automatically uploaded to a central website. The investigator or site designee should review the diaries and questionnaire data on the website to ensure completion and protocol compliance before each planned visit of the subject (on site visit or TC) and discuss the results or retrain the subject and/or subject's parent(s)/legal guardian(s)/caregiver(s), if applicable. In case clinically relevant adverse changes are noticed during review of the e-diary, these will be recorded as an AE [Appendix 12.4.1 Definition of Adverse Events].

The bladder e-diary, questionnaire results and other data collected in the e-diary will be transferred electronically to the sponsor or designee at predefined intervals during the study. The vendor will provide the sponsor or designee with a complete and clean copy of the study data. The ownership of this data is with the investigator and subsequently any changes requested to these subject-reported or nonsubject reported data will be made using the vendor's established process (e.g., a data clarification form to the vendor). The requested change must be supported by documented evidence at study site.

For this study the following information will be collected and entered by the subject or subject's parent(s)/legal guardian(s) in the e-diary (see [Sections 7.2.6 Acceptability and Palatability Questionnaire and 7.2.3.2 Self-measurement of Vital Signs] for detailed information per visit):

- Bladder e-diary:
 - Each day on weekend prior to week -2: volume measurements
 - Each day for 7 days before visit 3/week 0: micturition frequency
 - Each day for 7 days before visit 3/week 0: incontinence episodes
 - On the 2-day weekend period: volume measurements
- SBPM (blood pressure and pulse):
 - Each day of the 2-day weekend period: twice per day
 - On 2 consecutive weekend days at around 1 and 2 weeks after start of dosing with PED25 (day 1) and after up-titration to PED50, if not already covered by the scheduled SBPM
- Acceptability and Palatability Questionnaire:
 - On 1 weekend day preceding visit 7/week 12 (EoT)

The investigator must guide the subject and subject's parent(s)/legal guardian(s) to ensure that on the evening before and during the 2-day weekend period collection of volume, the subject's fluid intake should be regulated (as per investigator guidance) to an appropriate level considering, e.g., age, sex and subject's condition into account. The intake must remain as consistent as possible on these volume collecting days throughout the entire study.

- CONFIDENTIAL -

7.7 Other Assessments

Acceptability and palatability questionnaire will be completed on 1 weekend day preceding Visit 7/Week 12 (EoT). For each formulation a separate questionnaire is available, please see Appendices 12.8 Acceptability and Palatability Questionnaire for Tablets and 12.9 Acceptability and Palatability Questionnaire for Oral Suspension.

ISN/Protocol: 178-CL-204

Questionnaires are to be completed by the subject or the subject's parent(s)/caregiver(s) in the local language and provided via the e-diary. Results will be directly entered in the e-diary by the subject or subject's parent(s)/caregiver(s).

7.8 Total Amount of Blood

The total amount of blood for each subject will vary depending on the course of their disease, duration on treatment and central laboratory requirements. At any time during the study, if any laboratory abnormalities are found for a subject, additional blood may be drawn for safety monitoring.

The maximum blood volume to be collected within 24 hours is approximately 9.5 mL per subject on pharmacokinetic sampling days at visit 5/week 4 and visit 7/week 12 (EoT).

The total blood volume to be collected will be as follows

Table 8 Total Blood Volume per Subject over the Entire Study Period

| Sample Type | Number of Samples | Sample Volume (mL) | Total Volume (mL) |
|---|-------------------|--------------------|-------------------|
| Pharmacokinetics | 2 | 5.0 | 10.0 |
| Clinical Laboratory Tests† Biochemistry/hematology | 3 | 4.5‡ | 13.5 |
| Total | 23.5 | | |

[†] Additional hematology and biochemistry tests of approximately 4.5 mL total will be performed at visit 3/week 0 (baseline) and visit 8/week 14 (EoS) only if an adverse event related to hematology or biochemistry parameters occurred since the previous visit or at the discretion of the investigator. The total amount of blood drawn from subjects who require additional hematology and biochemistry tests due to AEs could be up to 32.5 mL.

8 DISCONTINUATION

8.1 Discontinuation of Individual Subject(s) From Study Treatment(s)

A discontinuation from treatment is defined as a subject who is randomized and for whom study treatment is permanently discontinued for any reason.

The subject is free to withdraw from the study treatment and/or study for any reason and at any time without giving reason for doing so and without penalty or prejudice. The investigator is also free to discontinue the participant from study treatment or to terminate a subject's involvement in the study at any time if the subject's clinical condition warrants it.

The reason for discontinuation from study treatment must be documented in the subject's medical records.

[‡] Volume does not take any unscheduled visits or repeat tests into account (e.g., follow up of adverse events).

Sponsor: APGD ISN/Protocol: 178-CL-204

A subject must discontinue study treatment for any of the following reasons:

- Subject requests to stop treatment.
- Any clinical AEs, laboratory abnormality or intercurrent illness, in the opinion of the investigator, indicates continued treatment is not in the best interest of the subject.
- If signs or symptoms of hypersensitivity to mirabegron are observed (e.g., anaphylactic reaction, erythema multiforme or exfoliative dermatitis).
- ALT or AST $> 8 \times ULN$.
- ALT or AST $> 5 \times ULN$ for more than 2 weeks.
- ALT or AST > $3 \times \text{ULN}$ and TBL > $2 \times \text{ULN}$ or international normalized ratio (INR) > 1.5 (if INR testing is applicable/evaluated).
- ALT or AST $> 3 \times$ ULN with the appearance of fatigue, nausea, vomiting, right upper quadrant pain or tenderness, fever, rash and/or eosinophilia (> 5%).
- Female subject becomes pregnant.
- Prolongation of QT > QTcF > 440 msec and/or QT interval prolongation > 30 msec versus baseline.
- Subject with (systolic blood pressure ≥ 160 mm Hg or diastolic blood pressure ≥ 100 mmHg.

If a subject discontinues treatment prematurely, the subject will be encouraged to complete all scheduled visits to record all available information.

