From the 9 subjects who completed the study (6 with NDO and 3 with OAB) 1 treatment emergent adverse event (TEAE) was reported: pyrexia on day 1 in an NDO subject. The intensity was mild and was judged by the investigator not to be related to study drug. No clinically significant electrocardiogram (ECG) abnormalities have been seen throughout the study, there were no QT interval using Fridericia's correction formula (QTcF) values > 450 msec and no QT interval prolongation > 30 msec versus baseline was observed (mean of triplicates).

A 24-hour continuous 12-lead ECG recording was recorded in all subjects on a reference day and on the dosing day. The main objective of the continuous 12-lead ECG recording was to evaluate the effect of mirabegron on heart rate in a time-matched manner, taking into account the circadian rhythm. A median increase in 24-hour heart rate of 5.1 bpm was observed. This was not considered as clinically relevant due to the multiple blood draws, the low number of subjects and the absence of a placebo treatment group.

Some changes in laboratory values were observed, but they were not considered as clinically relevant.

For Study 178-CL-208 single doses of 88 mg mirabegron oral suspension to adults were safe and well tolerated. Eleven of 24 subjects reported 22 adverse events (AEs). All except for 2 events (1 headache moderate and 1 dysmenorrhea moderate) were mild. Twenty AEs were considered not related; 2 were considered possibly related (dizziness, mild and orthostatic dizziness mild).

For study 178-CL-206A mirabegron tablets and oral suspension (8 mg/mL) once daily for up to 52 weeks, starting at PED25 and up-titrated to PED50 was generally well tolerated by pediatric patients in the completed clinical study. One of 86 (1.2%) patients (an adolescent) reported bradycardia. Using Fleming et al [2011], 3 of 50 (6.0%) children and 2 of 28 (7.1%) adolescents had potentially clinically relevant pulse rate readings during the study. Only 1 of 78 (1.3%) patients (a child) met the criteria for a TEAE of hypertension which was considered not related to the study drug by the investigator.

There were no clinically significant vital signs, clinical laboratory value or 12-lead ECG findings. Based on the mean visual analogue scale score for palatability, the suspension was acceptable in pediatric population and did not require further taste adjustment. The oral suspension when dosed in children was considered to be safe and well tolerated.

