2.1.3 Summary of Key Safety Information for Investigational Product(s)

Mirabegron has not been approved or marketed for use in pediatric subjects.

Detailed reference safety information (RSI) can be found in the Investigator's Brochure for mirabegron.

- CONFIDENTIAL -

Mirabegron has been approved in more than 81 countries worldwide. In adults, the safety of mirabegron treatment has been well characterized in 5863 subjects (95% with OAB) in the phase 2/3 registration studies treated with mirabegron at doses ranging from 25 to 200 mg once daily. Identified risks include increased heart rate and tachycardia, hypersensitivity reactions, increased blood pressure and urinary retention. Potential risks include QT prolongation, urinary tract infection (UTI), fetal disorders after exposure during pregnancy and events induced by concomitant treatment with cytochrome P450 2D6 (CYP2D6) substrates with a narrow therapeutic index. The risks of QT prolongation, increased heart rate or increased blood pressure are greater with increasing exposure at supratherapeutic doses and can be mitigated with optimal dose selection. The maximum therapeutic dose of mirabegron based on the overall benefit-risk is 50 mg once daily in adults.

ISN/Protocol: 178-CL-204

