- 13. Subject has QTcF > 440 msec on screening ECG, a risk of QT prolongation (e.g., hypokalemia, long QT syndrome [LQTS] or family history of LQTS or exercise-induced syncope) or is currently taking medication known to prolong the QT interval.

- CONFIDENTIAL -

14. Subject's aspartate aminotransferase (AST) or alanine aminotransferase (ALT) is \geq 2 × upper limit of normal (ULN) or total bilirubin (TBL) is \geq 1.5 × ULN according to age and sex (subjects with Gilbert's syndrome are excepted from the bilirubin threshold).

ISN/Protocol: 178-CL-204

- 15. Subject has mild or moderate renal impairment (estimated glomerular filtration rate according to the modified Schwartz of < 60 mL/min per 1.73 m²).
- 16. Subject has a symptomatic (symptoms can include pain, fever, hematuria, new onset foul-smelling urine) UTI. Note: if the UTI is treated successfully (clinical recovery: confirmed by dipstick test and repeated dipstick test after 14 days [both should be negative]), the subject can be rescreened.
- 17. Subject has a history or presence of any malignancy.
- 18. Subject uses any drugs that are sensitive cytochrome P450 2D6 (CYP2D6) substrates with a narrow therapeutic index, sensitive P-glycoprotein (P-gp) substrates, or moderate or strong cytochrome CYP3A4/5 or P-gp inhibitors or inducers after the start of washout.
- 19. Subject is using or has used prohibited prior and/or concomitant medication(s) [Appendix 12.6 List of Excluded Concomitant Medications] that cannot be discontinued.
- 20. Subject has known or suspected hypersensitivity to mirabegron or any components of the formulations used.
- 21. Subject has participated in another clinical study (and/or subject has received any investigational therapy within 30 days (or 5 half-lives of the drug, or the limit set by national law, whichever is longer) prior to visit 1/week -4 (screening).
- 22. Subject received urinary catheterization within 2 weeks prior to screening.
- 23. Subject has constipation as defined by the Rome IV criteria that cannot be successfully treated prior to study entry.
- 24. Female subject who has been pregnant within 6 months prior to screening or breastfeeding within 3 months prior to screening.
- 25. Subject has any condition, which in the opinion of the investigator, makes the subject unsuitable for study participation.

Additional Exclusion at Visit 3/Week 0 (Baseline)

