6.6 Dose Modification

At visit 5/week 4 (i.e., after 4 weeks on PED25), dose up-titration to PED50 will be performed unless the investigator determines that the subject is adequately treated for OAB at the PED25 dose or if there are safety concerns identified and considered associated with the use of PED25.

At any time, down-titration from PED50 to PED25 can be performed if there is an AE possibly related to the drug that is considered bothersome by the subject or that leads to medical intervention (e.g., initiation of medication therapy to treat the AE). Of note, PED25 is the lowest dose to be used in this study.

Criteria for discontinuation of individual subject(s) from study treatment are listed in [Section 8.1 Discontinuation of Individual Subject(s) from Study Treatment(s)].

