7.2.3 Vital Signs and Electrocardiograms

7.2.3.1 Clinic-measurement of Vital Signs and Electrocardiograms

Blood pressure (systolic blood pressure [SBP] and diastolic blood pressure [DBP]), pulse, and routine 12-lead ECG measurements will be taken as indicated in the Schedule of Assessments [Table 1].

The preferred method of measurement is via the auscultatory technique. If this method is not available at the study site, measurements will be per standard clinic practices. Single measurements of blood pressure, pulse, body temperature and ECGs will be measured in the sitting position (when possible, otherwise supine, but always in the same position). Subject should have been calm and without distress for at least 5 minutes. Preferably, the right arm should be used to measure vital signs. Body temperature will be measured with an ear thermometer as per standard of care. Clinic measurements will be used to assess eligibility.

For ECGs, dates and times may be generated by the machine's internal clock and are considered source data. The results are to be interpreted by qualified personnel in real time for the management of the subjects' clinical condition. The principal investigator/designee will initial and date and provide his/her clinical interpretation on each report. Any abnormalities must be evaluated in clinical context (based on subject's medical history and concomitant medication) and the investigator should determine if it is clinically significant. The results (normal, abnormal not clinically significant, abnormal clinically significant) are to be recorded in the eCRFs.

The original print-out and an electronic copy of all scheduled and unscheduled ECG tracings should be maintained on site as source data.

Clinic measurements will be used to assess eligibility. Clinically relevant adverse changes in vital signs and ECGs will be recorded as an AE (see [Appendix 12.4.1 Definition of Adverse Events]).

- CONFIDENTIAL -

ISN/Protocol: 178-CL-204

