10.3 Major Protocol Deviations

A protocol deviation is generally an unplanned excursion from the protocol that is not implemented or intended as a systematic change. All deviations from the protocol are to be recorded. A protocol waiver is a documented prospective approval of a request from an investigator to deviate from the protocol. Protocol waivers are strictly prohibited.

The investigator is responsible for ensuring the study is conducted in accordance with the procedures and evaluations described in this protocol and must protect the rights, safety and well-being of subjects. The investigator should not implement any deviation from, or changes of, the protocol, unless it is necessary to eliminate an immediate hazard to subjects.

A major protocol deviation is 1 that may potentially impact the completeness, accuracy or reliability of data contributing to the primary endpoint or affect the rights, safety or well-being of a subject. Major protocol deviations will have additional reporting requirements.

When a major deviation from the protocol is identified for an individual subject, the investigator or designee must ensure the sponsor is notified. The sponsor will follow up with

- CONFIDENTIAL -

the investigator, as applicable, to assess the deviation and the possible impact to the safety and/or efficacy of the subject to determine subject continuation in the study.

ISN/Protocol: 178-CL-204

The major protocol deviation criteria that will be summarized at the EoS are as follows:

- PD1 Entered into the study even though the subject did not satisfy entry criteria
- PD2 Developed withdrawal criteria during the study and was not withdrawn
- PD3 Received wrong treatment or incorrect dose
- PD4 Received excluded concomitant treatment

The investigator will also assure that deviations meeting IRB/IEC and appropriate regulatory authorities' criteria are documented and communicated appropriately. All documentation and communications to the IRB/IEC and appropriate regulatory authorities will be provided to the sponsor and maintained within the Trial Master File.

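### The mandatory QT stopping rule is mis-worded: its first limb is a drafting error for QTcF > 440 msec, and its second limb names no heart-rate correction

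*Protocol*

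**What the plan says.** Protocol 8.1 introduces its list with "A subject must discontinue study treatment for any of the following reasons". One entry is "Prolongation of QT > QTcF > 440 msec and/or QT interval prolongation > 30 msec versus baseline", and the synopsis repeats it word for word. Section 10.3 makes failure to act on the list a major deviation: "PD2 Developed withdrawal criteria during the study and was not withdrawn".

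The related text elsewhere is:

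- **Protocol 5.2, exclusion criterion 13:** "Subject has QTcF > 440 msec on screening ECG, a risk of QT prolongation". The metric and the cut-off are both clear here.
- **Protocol 2.1.2.2, on paediatric study 178-CL-203:** "no QT interval using Fridericia's correction formula (QTcF) values > 450 msec and no QT interval prolongation > 30 msec versus baseline was observed". The correction is named for the absolute value and not for the change.
- **Protocol 7.2.3.1, on who acts on the ECG:** "The results are to be interpreted by qualified personnel in real time for the management of the subjects' clinical condition".
- **SAP 5.4.5 and 6.5.4:** the ECG variables include QTcF but not raw QT, and change from baseline is tabulated for QTcF only.

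**The concern.** A mandatory stopping threshold should give the same answer whoever applies it. As printed, the first limb chains QT, QTcF and 440 msec into an inequality that is not a usable criterion. The second limb says only QT interval, so a site following the text could subtract one uncorrected QT from another.

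The choice matters for this drug. Protocol 2.1.3 says "Identified risks include increased heart rate and tachycardia, hypersensitivity reactions, increased blood pressure and urinary retention" and lists QT prolongation as a potential risk. A faster heart rate shortens raw QT, so the raw reading is the less protective one if heart rate rises on treatment.

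Timing matters too. In the Schedule of Assessments, week 4 is the only on-treatment ECG before the end-of-treatment visit. At that same visit, under 6.6, "dose up-titration to PED50 will be performed unless the investigator determines that the subject is adequately treated for OAB at the PED25 dose", or unless there are safety concerns. What is at stake is whether a child with a moderate QTcF rise at week 4 is stopped as the rule intends, and whether PD2 is counted consistently. The efficacy analysis is not at stake.

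**Working it through.** The plan gives no figure to reproduce for this rule. The check is a reading of the text followed by Fridericia's formula, QTcF = QT / (60/HR)^(1/3), so QT = QTcF × (60/HR)^(1/3).

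**Inputs**
- Median resting pulse of 98, 91 and 84 bpm at 4–6, 6–8 and 8–12 years, and 10th percentiles of 81, 74 and 67 bpm (SAP Table 4).
- Heart-rate rise of 5.1 bpm, the 24-hour median in study 178-CL-203 (Protocol 2.1.2.2). It comes from 9 completers with no placebo group and was judged not clinically relevant.
- Baseline QTcF of 400 msec. This is an assumption, since the documents give no value; 380 msec is shown as a variant.

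**Step 1: the first limb.** Exclusion criterion 13 has the same number with a clear metric, so the evident meaning is QTcF > 440 msec. The rest of the check uses that reading.

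**Step 2: where the second limb adds anything.** A QTcF rise above 30 msec from a baseline of 410 msec or more gives QTcF above 410 + 30 = 440 msec, which the first limb already catches. The wording of the second limb therefore matters only for a baseline below 410 msec.

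**Step 3: a rise that raw QT misses.** Baseline QTcF 400 msec at 84 bpm gives QT = 400 × (60/84)^(1/3) = 357.6 msec. Now let QTcF rise by 31 to 431 msec.
- At 84 bpm: QT = 431 × (60/84)^(1/3) = 385.3 msec, a change of +27.7 msec.
- At 89.1 bpm: QT = 431 × (60/89.1)^(1/3) = 377.8 msec, a change of +20.2 msec.

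Neither exceeds 30 msec. At medians of 91 and 98 bpm the constant-rate changes are +27.0 and +26.3 msec, and with the 5.1 bpm rise both are +20.2 msec. At baseline 380 msec and 91 bpm the two figures are +27.0 and +20.5 msec.

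**Step 4: width of the missed window.** Raw QT reaches +30 msec, that is 387.6 msec, at these points:
- Constant 84 bpm: QTcF = 387.6 / (60/84)^(1/3) = 433.6 msec, a rise of 33.6 msec.
- 89.1 bpm: QTcF = 387.6 / (60/89.1)^(1/3) = 442.2 msec, a rise of 42.2 msec.

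From 400 msec the first limb acts once the rise passes 40 msec. The missed window is therefore just above 30 to about 34 msec at constant heart rate, and about 31 to 40 msec with the 5.1 bpm rise.

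**Step 5: the opposite error.** With QTcF fixed at 400 msec, the heart rate that adds 30 msec of raw QT is 60 / ((QT + 30)/400)^3.

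| Age | Median HR | QT at median (msec) | HR giving +30 msec | Fall (bpm) | 10th percentile |
|---|---|---|---|---|---|
| 4–6 y | 98 | 339.7 | 76.0 | 22 | 81 |
| 6–8 y | 91 | 348.1 | 71.0 | 20 | 74 |
| 8–12 y | 84 | 357.6 | 66.0 | 18 | 67 |

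Each end rate is below the 10th percentile for age.

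**The case against.** The best case against the point is that the intent is plain. Exclusion criterion 13 settles the first limb. The second limb shares a sentence with QTcF, the list of adverse events of special interest (7.3.6) speaks of QTc prolongation, and the SAP carries no raw QT. No document tells a site to act on raw QT. All of this stands as evidence of intent. It does not fully answer the point, because SAP tables are not site instructions, and the line that binds a site reading an ECG in real time leaves the metric open.

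The safeguards also stand. Exclusion criterion 13 removes children already at QT risk. Investigators must stop treatment when they judge that an adverse event makes continuing unwise (8.1), and up-titration is withheld for safety concerns (6.6). QTc prolongation is reported within 24 hours (7.3.6), and the DSMB reviews safety (8.4).

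Three stronger readings are tempting, and the documents do not support them:

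- **The 440 msec threshold is inoperative in children.** Taken literally, QT exceeds QTcF only below 60 bpm, which is uncommon at these ages. Nothing suggests that a site would apply the line that way when exclusion criterion 13 supplies the meaning.
- **The rule prescribes raw QT, so sites will diverge.** The second limb is ambiguous. Divergence is possible but not shown.
- **Children would often be stopped with QTcF unchanged.** That needs a fall from the median to below the 10th percentile between two ECGs, each taken after at least five calm minutes. It also runs opposite to the drug's known effect on heart rate. Table 4 describes variation between children and says nothing about variation within a child.

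**Conclusion.** The rule is mis-worded and should be corrected. The severity is minor to moderate: it is a wording error in a mandatory safety criterion. The practical gap lies in the second limb, for a baseline QTcF below 410 msec, and only where a site chose raw QT. In the illustration that reading would miss QTcF rises of roughly 31 to 40 msec, which depends on the assumed 400 msec baseline, 84 bpm and a 5.1 bpm rise. With no change in heart rate the window shrinks to a few milliseconds. The opposite error is less likely.

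The number of children affected cannot be estimated, because the documents give neither baseline QTcF nor its within-child variability. A reader should not infer any effect on power, type I error or the efficacy estimate. Only protocol version 2.0 was available. SAP 5.4.2.1 and 5.4.6 allow for a version 3, which may already have corrected the line.

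**What to change.** In Protocol 8.1 and the synopsis, replace the entry with: *QTcF > 440 msec and/or increase in QTcF > 30 msec versus baseline*. First check it against the regulatory request that prompted the criterion (Attachment 1, nonsubstantial change 16) and against any later protocol version.

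The cost is one line in two places, with no added patients, procedures or SAP variables. The SAP summary bins use a change boundary of 30 msec or more, and adolescent cut-offs of 450 and 500 msec (male) or 480 and 500 msec (female). They describe data and need not match a stopping threshold, so aligning them is optional and not part of the error.
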